5.3 Packaging and Labeling

NewGam is delivered as ready-to-use solution in glass bottles.

Each NewGam bottle will be labeled as follows:

EU Master Label – NewGam:

FOR CLINICAL TRIAL USE ONLY NewGam	Study: NGAM-08 Unit size: _____ mL
1 mL contains: 100 mg protein of which $\geq 95\%$ is human normal immunoglobulin. Infusion solution for intravenous administration. To be stored at +2°C to +8°C and protected from light. Must not be frozen. Must be inspected visually for particulate matter and discoloration prior to administration. Do not use non-homogenous solutions or those that have a deposit. To be warmed up to room or body temperature before use. Dosage: see study protocol Section 5.5_ EudraCT number: 2015-005443-14 Investigator: _____ Sponsor: OCTAPHARMA PPG, [name], Tel:  CRO: _____ Batch no.: _____ Expiration date: _____	

Final labeling will be in compliance with the national requirements of each country where the study will be conducted.

After transfer and pooling into infusion bags, the medication (NewGam or 0.9% saline solution) will be blinded with an overpouch and re-labelled. The following labels will be used for sending the medication from the pharmacy/clinic to the ward:

EU Master Label – Overpouch for infusion bags:

FOR CLINICAL TRIAL USE ONLY	Study: NGAM-08
NewGam OR Sodium Chloride 0.9% w/v solution	Volume: _____ mL
1 mL contains: 100 mg protein of which $\geq 95\%$ is human normal immunoglobulin OR sodium chloride 0.9% w/v solution.	
Infusion solution for intravenous administration.	
To be stored at +2°C to +8°C (see study protocol Section 5.4). Must not be frozen.	
To be warmed up to room temperature before use.	
Dosage: see study protocol Section 5.5	
Pat. number: _ _ _ _ _ _	Infusion week: _ _ Bag number: _ of _
Date and time of preparation: _____	
Use by (date and time): _____	
Any unused solution residues or waste material to be disposed according to local requirements at the study site.	
EudraCT number: 2015-005443-14	
Investigator: _____	
Sponsor: OCTAPHARMA PPG, [name], Tel: 	
CRO: _____	

Final labeling will be in compliance with the national requirements of each country where the study is to be conducted.

5.4 Conditions for Storage and Use

NewGam should be stored and transported light-protected at +2°C to +8°C (36°F to 46°F) and must not be frozen.

NewGam must not be used after its expiration date.

Authorized personnel at the individual study centers/pharmacies will ensure that the IMPs are stored under appropriate conditions with restricted access and in compliance with national regulations.

5.5 Dose and Dosing Schedule

NewGam is available in glass bottles with different volumes of human immunoglobulin. Glass bottles of different content should be combined in order to reach the required amount of IgG (split into infusions of 0.5 g/kg and 1.0 g/kg to maintain blinding). The total amount per patient should be dosed exactly. Partially used bottles must be discarded.

All patients should be clinically assessed for being adequately hydrated prior to infusion.

In the Dose-evaluation Phase, all patients will receive a loading dose of 2.0 g/kg Newgam (administered over two consecutive days), followed by seven infusions of the maintenance dose the patient has been randomized to (0.5, 1.0 or 2.0 g/kg NewGam), also administered over two consecutive days every 3 weeks (± 4 days). If a patient is randomized to receive the low or medium NewGam dose, the same volume with the same infusion rate as would have been applied in case the patient would have been randomized to 2.0 g/kg NewGam will be used, thus

supplemented with an authorized 0.9% w/v isotonic sodium chloride solution as appropriate and detailed in the following infusion bag split to maintain the blinding:

Treatment Arms	Infusion Bag Content	
	Day 1	Day 2*
0.5 g/kg NewGam	0.5 g/kg NewGam + 0.5 g/kg saline	1.0 g/kg saline
1.0 g/kg NewGam	0.5 g/kg NewGam + 0.5 g/kg NewGam	1.0 g/kg saline
2.0 g/kg NewGam	0.5 g/kg NewGam + 0.5 g/kg NewGam	1.0 g/kg NewGam

* Volume of Day 2 may be split up using 2 bags

The following infusion schedule must be adhered to in the Dose-evaluation Phase [all doses per kg body weight; rescue treatment only for patients who had been on 0.5 or 1.0 g/kg NewGam before, patients on 2.0 g/kg before will drop-out]:

1. Patients deteriorating* after Week 3 and before Week 6 or being stable at Week 6**

Week 0	Week 3	Week 6	Week 9	Week 12
2.0 g (LD)	0.5g 1.0 g	2.0 g (RT)	2.0 g (RT)	EOS
	2.0 g	EOS		

2. Patients deteriorating* after Week 6 and before Week 9

Week 0	Week 3	Week 6	Week 9	Week 12	Week 15
2.0 g (LD)	0.5g 1.0 g	0.5g 1.0 g	2.0 g (RT)	2.0 g (RT)	EOS
	2.0 g	2.0 g	EOS		

3. Patients deteriorating* after Week 9 and before Week 12

Week 0	Week 3	Week 6	Week 9	Week 12	Week 15	Week 18
2.0 g (LD)	0.5g 1.0 g	0.5g 1.0 g	0.5g 1.0 g	2.0 g (RT)	2.0 g (RT)	EOS
	2.0 g	2.0 g	2.0 g	EOS		

4. Patients deteriorating* after Week 12 and before Week 15

Week 0	Week 3	Week 6	Week 9	Week 12	Week 15	Week 18	Week 21
2.0 g (LD)	0.5g 1.0 g	0.5g 1.0 g	0.5g 1.0 g	0.5g 1.0 g	2.0 g (RT)	2.0 g (RT)	EOS
	2.0 g	2.0 g	2.0 g	2.0 g	EOS		

5. Patients deteriorating* after Week 15 and before Week 18

Week 0	Week 3	Week 6	Week 9	Week 12	Week 15	Week 18	Week 21	Week 24
2.0 g (LD)	0.5g 1.0 g	0.5g 1.0 g	0.5g 1.0 g	0.5g 1.0 g	0.5g 1.0 g	2.0 g (RT)	2.0 g (RT)	EOS
	2.0 g	2.0 g	2.0 g	2.0 g	2.0 g	EOS		

LD – Loading Dose, RT – Rescue Treatment, EOS – End-of-Study-Visit

* = adjusted INCAT disability score increase of at least 1 point

** = adjusted INCAT disability score remains unchanged

5.7 Treatment Duration

In the Dose-evaluation Phase, all patients will receive a loading dose of 2.0 g/kg NewGam followed by seven times the dosage they were randomized to (0.5, 1.0 or 2.0 g/kg NewGam). Patients in the 0.5 and 1.0 g/kg NewGam arms being clinically stable until Week 6 (i.e. with unchanged adjusted INCAT disability score compared to baseline) will receive further infusions of 2.0 g/kg NewGam at Week 6 and 9, still keeping the blind. Patients who deteriorate (i.e. with increase in adjusted INCAT disability score of at least 1 point) after Week 3 and before Week 18 will receive two infusions of 2.0 g/kg NewGam at the next two consecutive 3-week intervals (earliest at Week 6 and latest at Week 21). Afterwards they will continue with the regular termination visit. Patients deteriorating after Week 18 will drop-out and have their Termination Visit at Week 21; patients deteriorating after Week 21 will drop-out and have their Termination Visit at Week 24.

5.8 Blinding, Emergency Unblinding and Breaking the Study Blind

The Investigators will be provided with an unblinding procedure to disclose the actual treatment of a particular patient in case of medical emergency. Blinding in individual patients should not be broken only in case of a serious adverse event or unexpected ADR, when knowledge of the type of the administered IMP is required for therapeutic decisions regarding this event. However the decision and the responsibility to break the treatment code in emergency situations resides solely with the investigator. In the event of medical emergency to keep subject safety, the investigator is able to unblind a patient immediately by accessing the IWRS system without needing a PIN code and without needing to contact any third party.

To maintain blinding in the Dose-evaluation Phase, infusions will be given in three infusion bags (corresponding to a volume of 0.5 g/kg, 0.5 g/kg and 1.0 g/kg NewGam or saline). Thus, the old label will be discarded together with the vial/bottle, and a new label will be fixed onto an opaque overpouch by the hospital pharmacist or designee. The order of the infusion bags will be added on the label: on Day 1 of an infusion visit the NewGam infusion bag (corresponding to 0.5 g/kg NewGam) comes first, then the second infusion bag (corresponding to 0.5 g/kg NewGam or matching saline) and last, at the following Day 2, the large infusion bag (corresponding to 1.0 g/kg NewGam or matching saline). Volume of Day 2 may be split up using two infusion bags instead of one.

An overpouch (normally used for light protection) will be put over each infusion bag to maintain blinding. The new labels will be identical for both, NewGam and saline, so that the content of the bags is only known to the unblinded hospital pharmacist or designee. An example of this label can be found above in [Section 5.3](#).

The hospital pharmacist or designee will send the 3 infusion bags per patient (potentially already fixed to the opaque infusion line) to the ward on the corresponding days. At the ward, the infusions will be given according to the order stated on the label (“1 of 3”, “2 of 3”, on Day 1 and “3 of 3” on Day 2). To further assure the double-blind character of this study, the physician or designee who applies the medication to the patient will not be involved in any other evaluations other than drawing blood samples or checking for vital signs, i.e. will not be involved in any patient ratings (e.g. INCAT, I-RODS, NCS, grip strength). In parallel, all Investigators for the electrophysiological or neurological evaluations will not be involved in the application of the medication.

Blinding of the patient: The patient will be blinded to the medication throughout the entire study. Because of the opaque (non-transparent) infusion line and overpouches, the patient will not be able to see the medication he/she is treated with.

Therefore, patients deteriorating (increase in adjusted INCAT disability score of at least 1 point) in the 0.5 and 1.0 g/kg NewGam arms after Week 3 and before Week 18 or remaining stable (unchanged adjusted INCAT disability score from baseline) by Week 6, and thus receiving 2 additional treatments with 2.0 g/kg NewGam, will continue with all study procedures as described in this protocol and will remain blinded as no serious safety issues are expected related to these procedures for patients continuing with NewGam treatment, while patients on 2.0 g/kg NewGam will drop-out if they deteriorate or are stable at Week 6.

The local study file will contain code break envelopes (or detailed instructions for the electronic equivalent thereof). If paper envelopes are used, the monitor will check the envelopes at each visit. Any breaking of the blind has to be documented with date, time, person, and reason.

The Investigator has to notify the Sponsor as soon as possible about the unblinding of a patient.

5.9 Subsequent Therapy

In case a patient decides to withdraw from the study or is withdrawn by the Investigator, he/she may continue with the treatment he/she has received before study participation or with another standard of care.

5.10 Relevant Protocol Deviations

Deviations from the protocol should not occur. If deviations occur, the Investigator should promptly inform the Monitor and the implication of the deviation must be reviewed and discussed. Any deviation must be documented, stating the reason and date, the action taken, and the impact for the patient and/or the trial. The documentation must be kept in the Investigator's Trial File and the Sponsor's file.

Examples of relevant protocol deviations that will be addressed are:

- Patients who entered the study even though they did not satisfy the entry criteria
- Patients who developed withdrawal criteria during the study
- Patients who received the wrong treatment or incorrect dose
- Patients who received an excluded concomitant treatment (e.g. IGIV other than NewGam).

In case of any major protocol deviations or violations the Investigator and Octapharma will decide on the further participation of the patient in this study, after having discussed all relevant aspects.

A list of all included patients with all deviations from the intended study procedures and other criteria that may affect the patient's validity for statistical analysis will be prepared upon clinical completion of the study. This will then be discussed by a panel consisting of the clinical project manager, a medical expert of the Sponsor, the data manager, the study biometrician and the Steering Committee. This panel will decide upon the membership of the patient in the ITT and PP efficacy and safety populations for statistical analysis.

6 STUDY CONDUCT

A signed informed consent form must be available before the start of screening activities.

The schedule of all visits is applicable for all patients of all treatment arms.

6.1 Observations by Visit

6.1.1 Screening (Visit 1; duration up to 21 days, i.e. Week -15 to -12)

Patients have to be informed about the study details and have to give their written informed consent. Prior to treatment initiation, patients will have to be screened for eligibility (inclusion and exclusion criteria). This includes general physical/neurological examination, vital signs and medical history assessment. Also, electrophysiological recordings (NCS of 4 right sided and 4 left-sided motor nerves) to confirm the diagnosis of definite or probable CIDP will be done as part of the in-/exclusion criteria evaluation. Women of childbearing potential (WOCBP) must have a negative pregnancy test to be eligible for the study. At Visit 2, 3, 4, 5, 6, 7, 8, 9 and Termination Visit a pregnancy test should be performed only if required by local requirements.

If feasible, screening should be completed within three weeks. However, screening results should be available as soon as possible but might take up slightly longer until also the results of the centrally evaluated NCS (by [REDACTED]) become available. Based on the screening results, the patients' eligibility for the study is determined, and a patient could proceed with the Wash-out Phase, if he/she is eligible.

Screening failures will be entered into the eCRF.

The following assessments will be performed during screening:

- Obtaining voluntarily given, written (signed and dated) informed consent
- Medical history and prior/concomitant medication
- Physical/neurological examination
- Vital signs (including body weight and height)
- Inclusion and exclusion criteria
- Standard ECG
- Urinalysis
- Blood sample (5 mL) for viral markers
- Blood samples (10 mL) for safety laboratory (hematology and clinical chemistry)
- Pregnancy test
- Grip strength
- Adjusted INCAT disability score
- I-RODS
- MRC sum score
- Modified FSS
- PI-NRS
- NCS
- SF-36

6.1.2 Procedures During the Wash-out Phase of the Study

Eligible patients will have to enter a Wash-out Phase of up to 12 weeks, i.e., they have to decrease their current medication (immunoglobulins or corticosteroids; see Section 3.2). In this Phase the medication will successively be reduced until the patient deteriorates.

For patients on corticosteroids, no scheduled or required study evaluations/visits will take place during the Wash-out Phase. However the patients must inform the investigator whenever they notice any symptom of disease worsening at any time during the Wash-out Phase and must come to the site for assessment of deterioration. If deterioration cannot be confirmed, the Wash-out Phase will continue.

Patients on immunoglobulin treatment will have to visit the study site (e.g. IGIV every three weeks) for their infusions. Thus, from these patients concomitant medications and AEs will be recorded.

6.1.3 Procedures During the Dose-evaluation Phase of the Study

Only patients who deteriorate during the Wash-out Phase (active patients) will visit the study site and enter the Dose-evaluation Phase after randomization. All other patients who do not have active disease will not be eligible for enrollment into ProCID and will discuss their further treatment possibilities with their treating physician.

Visit 2 (Week 0; up to 12 weeks after Screening end; Baseline for Dose-evaluation Phase)

All patients who deteriorate during the Wash-out Phase will be rechecked for eligibility and, if positive, will be treated with 2.0 g/kg NewGam. At this time they will also be randomized to one of three NewGam dosages employed. The following assessments will be performed:

Before infusion:

- Physical/neurological examination
- Confirm eligibility (in-/exclusion criteria)
- Randomization and enrollment
- Blood sample (5 mL) for viral markers
- Blood samples (15 mL) for safety laboratory (serum IgG, hematology and clinical chemistry)
- Grip strength
- Adjusted INCAT disability score
- I-RODS
- MRC sum score
- Modified FSS
- PI-NRS
- NCS
- PGIC scale

During and after infusion:

- Administration/Infusion of IMP (2.0 g/kg NewGam)
- SF-36 (during infusion)

- Vital signs (including body weight) before, at least once during and after infusion
- Monitoring of adverse events (AEs)
- Documentation of concomitant medication

Visits 3, 4, and 5 (Week 3, 6, and 9)

The following assessments will be performed:

Before infusion:

- Blood sample(s) (15 mL) for safety laboratory (serum IgG, hematology and clinical chemistry)
- Grip strength
- Adjusted INCAT disability score
- I-RODS
- PI-NRS

During and after infusion:

- Administration/Infusion of IMP (0.5, 1.0 or 2.0 g/kg NewGam)
- Vital signs before, at least once during and after infusion
- Monitoring of adverse events (AEs)
- Documentation of concomitant medication

Visit 6 (Week 12)

The following assessments will be performed:

Before infusion:

- Physical/neurological examination
- Blood samples (15 mL) for safety laboratory (serum IgG, hematology and clinical chemistry)
- Grip strength
- Adjusted INCAT disability score
- I-RODS
- MRC sum score
- Modified FSS
- PI-NRS
- NCS

During and after infusion:

- Administration/Infusion of IMP (0.5, 1.0 or 2.0 g/kg NewGam)
- SF-36 (during infusion)
- Vital signs (including body weight) before, at least once during and after infusion
- Monitoring of adverse events (AEs)
- Documentation of concomitant medication

Visits 7, 8 and 9 (Week 15, 18 and 21)

The following assessments will be performed:

Before infusion:

- Blood sample(s) (15 mL) for safety laboratory (serum IgG, hematology and clinical chemistry)
- Grip strength
- Adjusted INCAT disability score
- I-RODS
- PI-NRS

During and after infusion:

- Administration/Infusion of IMP (0.5, 1.0 or 2.0 g/kg NewGam)
- Vital signs before, at least once during and after infusion
- Monitoring of adverse events (AEs)
- Documentation of concomitant medication

End of Study (Final) Examination

The final examination is performed three weeks after the last IMP administration (regularly at Visit 10 scheduled for Week 24 for responders), which can be either the last dose as randomized, or the last rescue dose.

The following investigations will be performed:

- Physical/neurological examination
- Blood sample (5 mL) for viral markers
- Blood samples (15 mL) for safety laboratory (serum IgG, hematology and clinical chemistry)
- Urinalysis
- Grip strength
- Adjusted INCAT disability score
- I-RODS
- MRC sum score
- Modified FSS
- PI-NRS
- NCS
- SF-36
- Monitoring of adverse events (AEs)
- Documentation of concomitant medication

After the Final Examination, the clinical study is considered completed for the patient. No further study-related assessments will be performed, unless safety concerns (e.g., ongoing AEs) require follow-up.

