
 • Time to first confirmed worsening on the adjusted INCAT disability scale by at least 1 point from the value at baseline (Week 0) • Mean change from baseline (Week 0) to Termination Visit in 
 ○ grip strength of both hands (assessed by Martin Vigorimeter) ○ Inflammatory Rasch-built overall disability sum score (I-RODS using the concept of MCID-SE as recently reported; Appendix 1) and number of improvers ○ sum of the distal evoked amplitude of 4 right sided and 4 left sided motor nerves (peroneal, tibial, ulnar and median) ○ Pain Intensity Numeric Rating Scale (PI-NRS) • Time to first confirmed worsening on the I-RODS scale • Time to 1 point decrease (improvement of disability) in adjusted INCAT disability score • Time to decrease in I-RODS scores 
Exploratory
 
 • Mean change from baseline (Week 0) to Termination Visit in: 
 ○ modified Fatigue Severity Scale (FSS; 7-item scale from 0-21 points; see Appendix 2) ○ number of improvers by at least 4 points in the MRC sum score (according to the universal rule of minimal clinical important difference) ○ SF-36 Health Survey physical composite score (PCS), mental composite score (MCS) and their 8 health domains (see Appendix 3) ○ additional NCS analyses (e.g. individual nerve analysis) • Time to decrease in MRC sum score to or below baseline value after temporary improvement (increase) 
Safety (throughout the entire Wash-out and Dose-evaluation Phases):
 
 • Occurrence of all adverse events (AEs) • Short term tolerance parameters including vital signs • Physical/neurological examination • Laboratory parameters (hematology and clinical chemistry) and tests for viral safety 	
Summary of Study Procedures and Statistical Analysis Plan:	
Study Procedures:	
Disability will be assessed by the adjusted INCAT score and the I-RODS at each visit.	
Pain will be assessed by the PI-NRS at each visit.	
Impairment will be assessed by the grip strength at each visit, MRC sum score and the modified FSS (Fatigue Scale) at Screening, Week 0, Week 12 and Termination Visit.	
Quality of life (SF-36) will be measured at Screening, Week 0, Week 12, and at Termination Visit.	

Name of Sponsor/Company: Octapharma Pharmazeutika Produktionsges.m.b.H., 1100 Vienna, AT	

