1.2 Benefit-Risk Statement

Currently, the optimal dosage of IGIV for treatment of CIDP patients is not known and has never been systematically examined. Historically, a dose of 1.0 g/kg has been used in the largest and longest placebo-controlled study that led to approval of the first IGIV for CIDP.[24] Later studies usually relied to this dosage scheme.[25] However, there may be additional benefits to individuals and society from this trial (ProCID: “**Progress in CIDP**”) in which the lack of dose response data in the literature will be addressed more extensively. There might be the possible benefit of a potential finding of this trial that a lower dose is beneficial for most patients resulting in less risk of adverse treatment effects for patients and lower costs for healthcare systems. On the other hand, it could also indicate that a higher dose might increase the number of patients who benefit from IGIV treatment, thus, reducing the number of non-responders.

The risks of IGIV administration are well documented. In general, the incidence of AEs associated with IGIV tends to increase with the rate of infusion, and thus the recommended dosage, infusion rates, and monitoring procedures should be adhered to. Patients naïve to IGIV are at higher risk compared to those who are well maintained and on regular therapy.

Patients with pre-existing risk factors for thrombotic events (such as advanced age, obesity, hypertension, diabetes mellitus and a history of vascular disease or thrombotic episodes, patients with acquired or inherited thrombophilic disorders, patients with prolonged periods of immobilization, severely hypovolemic patients, patients with diseases which increase blood viscosity) may be at risk.

When medicinal products prepared from human blood or plasma are given to a patient, the transmission of infectious agents cannot be totally excluded. This applies also to hitherto unknown pathogens. However, specific virus inactivation procedures are implemented in the manufacturing process of NewGam which are described in detail in the Investigator's Brochure.

The safety profile of NewGam is well characterized. For NewGam, the same type of adverse reactions has been seen as with other IGIV products. No new or unknown safety problems are expected to emerge which are not already described in the Investigator's Brochure.

In terms of efficacy, it can reasonably be assumed that NewGam exhibits the same effectiveness as other IGIV brands.

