3.1.3 Exploratory Endpoints

Efficacy:

Mean change from baseline (Week 0) to Termination Visit in:

- modified Fatigue Severity Scale (FSS; 7-item scale from 0-21 points; see [Appendix 2](#))
- number of improvers by at least 4 points in the MRC sum score (according to the universal rule of MCID [28] at Week 12 or at time of rescue NewGam infusion [26])
- SF-36 Health Survey physical composite score (PCS), mental composite score (MCS) and their 8 health domains (see [Appendix 3](#))
- additional NCS analyses (see Section 7.2.3.4)

Time to decrease in MRC sum score [29] to or below baseline value after temporary improvement (increase)

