Overall patient response is defined as follows:

Yes, if clinically important improvement (i.e. MCID-SE ≥ 1.96) at week 24 and patient did not receive rescue treatment; No otherwise (including patients discontinued before week 24 and patients receiving rescue treatment).

Response based on the original MRC sum score [at Week 24]:

Yes, if increase from Week 0 by at least 4 points and patient did not receive rescue treatment; No otherwise (including patients discontinued before week 24 and patients receiving rescue treatment)

An analogue definition will be applied for response at Week 12.

Worsening based on the original MRC sum score:

Decrease to or below baseline value after temporary improvement by at least 4 points. Patients who did not temporarily improve by at least 4 points will be excluded from the analysis of time to first worsening.

Changes from baseline to termination visit in scales/scores:

When calculating those changes, values under rescue treatment will not be taken into account. Changes will be calculated to last value before start of rescue treatment.

• MRC sum score:

Though mentioned in the protocol, a modified version of the MRC sum score will not be calculated, as this modified version could not be established in other studies.

NCS measurements:

The following variables will be calculated from NCS measurements:

- Sum of all distal amplitudes: the sum will be calculated from 4 nerves, both right and left sides, for a total of 8 amplitudes. The distal sites are the ankle (lower limbs, peroneal and tibial nerves) and wrist (upper limbs, ulnar and median nerves).
- Sum of the proximal amplitudes: this will be a total sum of 6 parameters, as no proximal amplitude was measured for the tibial nerve. Proximal sites are at the fibular head (lower limb peroneal nerve) and elbow (upper limbs).
- Sum of conduction velocities (6 in total, as no conduction velocity was measured for tibial nerve)
- Sum of durations distal locations (8 in total)
- Sum of areas distal locations (8 in total)

For the last three variables, in case the result is NR (No response) in the data set, the worst value in the data set for the corresponding parameter and for the respective nerve will be used. Worst value is the highest value for durations, lowest value for area and lowest value for conduction velocity.

9. Study Subjects and Demographics

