10.2. Secondary and Exploratory Efficacy Variable Analysis

All efficacy endpoints detailed in section 3.2 will be summarized by means of descriptive statistics, presented graphically as appropriate, and listed in full detail. Tables and graphs will allow for direct comparison of the different dose groups. If data are tabulated by dose group, the presentations will also include a total category, summarizing the data of all subjects in any of the dose groups. Tables for changes from baseline will include 95% confidence intervals of the mean for continuous secondary endpoints (I-RODS total score; grip strength; MRC sum score; FSS total score; NCS measurements; QoL scores) and 95% confidence intervals for the median for ordinal scales (INCAT disability sore, PI-NRS), calculated with PROC univariate option CIQUANTDF.

Similar analyses as for the primary endpoint will be performed for response variables defined based on secondary endpoints (I-RODS, grip strength, MRC sum score). These will include analysis of response rates and 95% confidence intervals, logistic regression models using the same factors as for the primary endpoint, Kaplan-Meier analyses for time to response and time to first worsening and response rates after having provided rescue medication.

Moreover, ANCOVA models will be applied for continuous secondary endpoints (I-RODS total score; grip strength; MRC sums score; FSS total score; NCS measurements; QoL scores). These ANCOVA models for changes from baseline to end of study will include dose group, randomization stratum and CIDP variant as factors and baseline value of the score/measurement as covariate. ANCOVA models will be used for calculation of least square means in various subgroups as well as for calculation of difference in least square means between the factor levels. All least square means will be presented together with 95% confidence intervals.

Any deterioration during the dose evaluation phase will be listed. Moreover, deteriorations during dose evaluation will be presented by dose group and by their effect on subject disposition (discontinuation, rescue medication).

11. Safety and Tolerability Analyses

The analysis of safety assessments in this study will be presented for the SAF.

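### The Week 0 SF-36 is completed during the loading infusion and the Termination SF-36 is not, so the planned exploratory change to Termination has no pre-treatment baseline and mixes assessment conditions

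*Protocol*

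**What the plan says.** The protocol synopsis sets the schedule for the quality-of-life form: "SF-36) will be measured at Screening, Week 0, Week 12, and at Termination Visit". Section 6.1.3 sets the timing within each visit. At Visit 2 (Week 0) and Visit 6 (Week 12) the form sits in the list of procedures for during and after the infusion, with the entry "SF-36 (during infusion" both times. At those visits the adjusted INCAT score, I-RODS, modified FSS, PI-NRS and grip strength are all in the pre-infusion list.

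At the end of study the SF-36 carries no timing note, and no infusion is given: "The final examination is performed three weeks after the last IMP administration".

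Protocol section 3.1.3 defines the exploratory endpoint as "Mean change from baseline (Week 0) to Termination Visit in", among others, "SF-36 Health Survey physical composite score (PCS), mental composite score (MCS) and their 8 health domains". Section 7.2.3.5 makes the physical summary score the principal SF-36 analysis. SAP section 10.2 says "ANCOVA models will be applied for continuous secondary endpoints" and counts the quality-of-life scores among these, with the baseline value as covariate. For rescued patients, SAP section 8.4 disregards values under rescue: "Changes will be calculated to last value before start of rescue treatment". Neither document gives a reason for the SF-36 timing.

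**The concern.** A baseline should be recorded before study treatment starts. The SF-36 is the only patient-reported scale here whose Week 0 value is recorded after the loading dose has begun. Modified FSS has the same four-visit schedule and the same exploratory status, yet is completed before the infusion.

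If being on an infusion moves the answers, that movement is in the baseline but not in the Termination value, and it passes into the reported within-arm change. The protocol itself expects some infusion effects. Section 1.2 says that "the incidence of AEs associated with IGIV tends to increase with the rate of infusion" and that patients new to IGIV are at higher risk. Patients from the corticosteroid stratum may be among these. Relief at being treated after a deterioration could push the answers the other way.

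The timing also meets the rescue rule. A form filled in during the first rescue infusion is no longer a value from before rescue.

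**Working it through.** There is no planned figure to reproduce, because the documents give no SF-36 mean, SD or target difference. The check sets the timing in protocol section 6.1.3 against the rescue schedules in section 5.5 and the rule in SAP section 8.4. Under section 6.1.4, rescue visits follow the procedures of the corresponding scheduled visit, so the start of rescue does not add an SF-36.

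| Patient's course | End value under SAP 8.4 | Week 0 / end value |
|---|---|---|
| Not rescued, reaches Week 24 | Termination | on / off |
| 2.0 g/kg arm, leaves early at an end-of-study visit | End-of-study visit | on / off |
| Rescue starts at Week 15 or 18 | Week 12 | on / on |
| Rescue starts at Week 12 | None: the Week 12 form is completed during the first rescue infusion | no usable change |
| Rescue starts at Week 6 or 9 | None: no SF-36 is due between Week 0 and Week 12 | no usable change, whatever the timing |

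The Week 0 to Week 12 change is on / on. In the fourth row, FSS and I-RODS are recorded before the Week 12 infusion and stay usable, so the SF-36 is lost through its timing alone. Read literally, the last value before rescue for that patient is the Week 0 value itself, which would give a change of zero by construction. The SAP does not say whether that is meant.

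**Effect of a baseline shift.** Let B be the score a patient would give before the infusion, T the Termination score, and d the mean shift from answering during the infusion.

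- Recorded baseline: B* = B + d. Recorded change: T − B* = (T − B) − d. Each arm's mean change moves by −d.
- Difference between two doses: (C₂ − d) − (C₁ − d) = C₂ − C₁, where C₁ and C₂ are the arms' true mean changes. A constant d cancels.
- ANCOVA: replacing B by B + d alters only the intercept. Each arm's least square mean moves by −d, and the differences between doses do not move. All arms receive the same 2.0 g/kg loading dose, blinded, so d has no reason to differ by arm except by chance.
- Residual through rescue: rescue exists only in the 0.5 and 1.0 g/kg arms. Suppose a share p of an arm's usable changes is on / on, and the shift at Week 12 equals d. That arm's mean moves by −(1 − p)d. Against an arm with p = 0, the difference is −(1 − p)d + d = pd. The documents give no expected rescue rate, so p is unknown; under this assumption the residual cannot exceed d in size.

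**Illustration (assumed inputs).** Take an SD of change of 6 to 10 points and n = 70, the enrolment target for the 1.0 g/kg arm. The standard error is SD/√70: 6/8.37 = 0.72 and 10/8.37 = 1.20.

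| Assumed d | Movement of within-arm mean change | In standard errors |
|---|---|---|
| −2 | +2 (improvement overstated) | 2/1.20 = 1.7 to 2/0.72 = 2.8 |
| 0 | 0 | 0 |
| +2 | −2 (improvement understated) | 1.7 to 2.8 |

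The usable n will be below 70, because patients rescued at Week 6, 9 or 12 have no usable change. That raises the standard error and lowers these ratios.

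**The case against.** The strongest reply is that this hardly matters. The SF-36 is exploratory, and the only confirmatory test is on INCAT response. The other patient-reported scales are taken before the infusion. The mechanism also requires answers that reflect the patient's state at that moment. The questionnaire is in Appendix 3, of which only the title is available here, so its recall wording cannot be checked. The remark in section 1.2 is about adverse events and infusion rate, not quality of life, and section 5.6 starts each infusion at the lowest rate. All of this stands. It limits the severity and leaves the shift unquantified, but it does not turn the Week 0 value into a pre-treatment one or explain why this scale is handled differently.

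Three stronger readings are tempting, and the documents do not support them.

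- A reader might infer that every SF-36 change from baseline is mismatched. The change to Week 12, and the change for patients rescued from Week 15 or 18, are on-infusion at both ends.
- A reader might infer that the dose comparison is biased. The common loading dose removes a constant shift, and only the residual pd remains.
- A reader might infer that Week 12 scores are distorted by arm, because Day 2 is saline in two arms and NewGam in the third (section 5.5) and the day of the form is not fixed. Protocol section 3.1.3 and SAP section 3.2.2 name no Week 12 contrast for the SF-36. Volumes and rates are matched and the bags and lines are masked. Nothing in the documents links bag content to SF-36 answers.

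**Conclusion.** The point holds as a minor one. For patients whose Termination value is used, the planned exploratory SF-36 change rests on a baseline taken after study drug has started and compares an on-infusion value with an off-infusion one. This concerns ten reported scores: two composites and eight domains. Within-arm change moves by the unknown shift d, in either direction or not at all. The claim that benefit is overstated would need a negative d, which the documents do not establish. Contrasts between doses are largely protected, on the assumption that d does not depend on arm.

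One consequence needs no assumption about d: with the form completed as scheduled, rescue starting at Week 12 leaves a patient without a usable SF-36 change, while FSS and I-RODS survive.

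**What to change.** In protocol section 6.1.3, Visits 2 and 6, move the SF-36 to the pre-infusion list with I-RODS, modified FSS and PI-NRS, and delete the during-infusion note. This gives a pre-treatment baseline, matches conditions with Termination, and keeps the Week 12 form usable when rescue starts that day. The cost is a short wording amendment and a few more minutes before the infusion at two visits.

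For data already collected, amend the SAP before unblinding:

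- State that within-arm SF-36 change to Termination compares on-infusion with off-infusion values, and should be read with that limit.
- Present the Week 0 to Week 12 change alongside it as the contrast matched on infusion status, noting that bag content at Week 12 differs by arm.
- State how a Week 12 SF-36 is handled when rescue starts at that visit, including whether the Week 0 value may stand in for it.

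A sensitivity analysis that omits forms completed during infusion would not help. If sites followed the protocol, it removes essentially every baseline. The only earlier SF-36 is at Screening, before wash-out and deterioration, and is not an equivalent baseline. The SAP changes cost some text and one additional table.
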